Enrollment and Sample Size. As mentioned above, we will aim to enroll 16-20 Veterans in RAP and another 16-20 Veterans in the Hatha yoga program, for a total recruitment target of 32-40 Veterans. Looking back 3 months, we estimate that there are approximately 1,500 Veterans at Hines who meet our study eligibility criteria. Accordingly, we do not anticipate having any difficulties identifying and enrolling enough patients to meet this target. However, if needed we will expand our time-frame to include Veterans who received the

relevant diagnoses in the previous 6, 9 or 12 months. Of note, goals for aims 2 and 3 include determining feasibility numbers for recruitment and estimates of effect sizes to inform power considerations for the next step, the larger trial.

Data Collection. Our data collection instruments reflect the factors that influence behavior as outlined in our conceptual framework; the relevant factors are noted in *italics* next to relevant questions in the appendices. Outcomes and strategies for measuring each are described below and summarized in Table 1.

Pre- and Post- Program Participation Surveys. All Veterans who are enrolled into the study will receive a pre-participation survey (Appendix D) approximately 1 week before the RAP/Hatha yoga classes begin, and a post-participation survey approximately 1 week after the 12-week programs are finished (Appendix E). Surveys will be mailed to Veterans so that persons who do not attend the first class of the program they are randomized to or do not complete

the program still have the opportunity to fill out a survey. This will allow us to also compare outcomes between individuals who did and did not complete the programs. Veterans will also be given the option to complete the surveys over the phone with the study project manager, and we will follow up with Veterans who do not return a mailed survey by phone to

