optimize response rates. We will also provide Veteran to complete the baseline survey in-person at the time of study enrollment. Veterans who attend the first and last yoga class of each session will also be provided an opportunity to complete the survey in person at their preference. Veterans will receive \$25.00 in appreciation of their time for each returned survey (up to two total surveys). Of note, we will not provide any token incentives for completing the yoga programs because we do not want to contaminate adoption rate data such that we cannot tease out whether Veterans are participating because they like the program or because they want to complete the program so that they can earn the incentive.

The surveys will include measures of pain intensity; pain behavior; function; quality of life (QOL); sleep; depression; stress; medication (and other pain reduction strategy) use, and; patient perceptions of and experiences with the program.

Pain intensity will be measured using the Defense and Veterans Pain Rating Scale,⁵ a valid and reliable numeric rating scale that asks individuals to report the average intensity of their low back pain on a scale of 0 (no pain) to 10 (worst pain imaginable)⁶ for the previous 7 days.

Pain interference (how much the individual's pain has interfered with all aspects of their life in the prior 7 days) will be measured using the validated, reliable Patient-Reported Outcomes Measurement Information System (PROMIS) 8-item pain interference short form.⁷ PROMIS scores are standardized to reflect the general adult US population, such that a mean score of 50 reflects average pain experience; higher scored indicate greater levels of pain interference.

Back pain-related function will be measured using the Roland-Morris Disability Questionnaire (RMDQ), a valid and reliable scale of physical disability resulting from chronic low back pain.⁸ The RMDQ asks individuals to read 24 items noting back pain-related functional impairments and mark those that describe them. All marked items are summed for a total score ranging from 0 (no impairment) to 24 (maximum impairment). A 30% reduction in score from baseline coupled with an improved self-reported pain intensity rating is considered a clinically significant impact.⁹

Health-related QOL will be measured using the Medical Outcomes Study 12-Item Short Form Health Survey (SF-12),¹⁰ a valid and reliable measure that produces physical and mental health sub-scale scores.

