Quantitative Analysis of Surveys. We will use descriptive statistics (proportions, means) to assess adoption, sustained engagement, and pain and related outcomes. All outcomes will be scored based on the guidelines of each respective measure. Rates of adoption (e.g., program initiation, defined as the number of Veterans who start the RAP or Hatha yoga programs after being screened, deemed eligible for participation, and randomized to one or the other) and sustained engagement (e.g., participation, defined as the average number of classes Veterans attended for each respective program, and the number of Veterans who attended the majority (9/12) of classes), will be compared for the RAP and traditional yoga groups using bivariate analyses (t-tests, chi-square tests), to determine if initiation and participation rates are statistically significantly higher for the RAP vs. Hatha yoga groups (Hypothesis 1). We will use bivariate analyses (t-tests) and ANOVA to compare outcomes (pain intensity; pain behavior; function; QOL; sleep; depression; stress; medication (and other pain reduction strategy) use) (1) for each Veteran before and after program participation, and (2) between Veterans in the RAP vs. traditional yoga programs. We will also compare all outcomes by gender. We will calculate effect sizes for all bivariate comparisons. As mentioned above, our goals for aims 2 and 3 include determining feasibility numbers for recruitment and estimates of effect sizes to inform power considerations for the next step, the larger trial. We will use our adoption and participation rates to base recruitment and enrollment targets for that trial, and will base power calculations off of the effect sizes on key outcomes (e.g., pain intensity, interference, back-pain related function) observed in this pilot. Survey data on patient experiences with and perceptions of the programs, assessed in part via open-ended questions on the post-program participation survey, will be content coded by [name] and the qualitative research specialist and triangulated with interview data under the guidance of [name] (please see below).

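### The between-arm comparison of continuous survey scores names no baseline covariate and leaves its form open, giving up modest precision and leaving the effect-size scale for the next trial undefined

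*Combined protocol and SAP*

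**What the plan says.** The only analysis text for the survey scores is Quantitative Analysis of Surveys, under Data Analyses. It states: "We will use bivariate analyses (t-tests) and ANOVA to compare outcomes". That one phrase covers both the before/after comparison within Veterans and the comparison between arms. No covariate, regression model or response variable is named. The section adds "We will calculate effect sizes for all bivariate comparisons", and for the larger trial the team "will base power calculations off of the effect sizes on key outcomes (e.g., pain intensity, interference, back-pain related function) observed in this pilot".

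A baseline score is planned in both randomized arms. Under Pre- and Post- Program Participation Surveys, "All Veterans who are enrolled into the study will receive a pre-participation survey" about a week before classes start. The completion route varies. Surveys go by mail, with a phone option; Veterans may also "complete the baseline survey in-person at the time of study enrollment"; and "Veterans who attend the first and last yoga class of each session will also be provided an opportunity to complete the survey in person". The documents do not say when a Veteran learns the assignment relative to the baseline survey.

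The outcome lists do not agree. The survey list begins "The surveys will include measures of pain intensity; pain behavior; function; quality of life (QOL" and never names pain interference, and the list of compared outcomes in the analysis section has the same gap. Yet the survey section describes an instrument for pain interference and none for pain behavior, Table 1 lists both, and the analysis section names interference among the key outcomes for powering the next trial.

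**The concern.** In a randomized comparison, a baseline measure of the outcome is usually the most useful covariate. A post-score t-test does not use it. A change score, or the group-by-time term of a repeated-measures ANOVA, uses it with a slope fixed at 1. ANCOVA estimates the slope and is the more precise analysis over the usual range of correlations. With 32 to 40 Veterans, information already collected is worth using.

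Two things are at stake. The first is the precision of the between-arm differences in pain intensity, interference and function that will feed the next trial's power calculation. The second is the meaning of those effect sizes: one mean difference gives different standardized values when divided by a post-score SD, a change-score SD or a residual SD, and the plan does not say which it will use.

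**Working it through.** **Inputs from the documents.** Two programs, two sessions each, 8 to 10 Veterans per session (Class Size): 2 × 2 × 8 = 32 and 2 × 2 × 10 = 40. This reproduces the stated target of 32-40, or n = 16 to 20 per arm. The plan gives no alpha, power, SD or target difference to reproduce.

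**Assumptions, not in the documents.** Baseline-to-post correlation ρ of 0.3, 0.5 or 0.7; equal SD before and after (set to 1); full survey return; two-sided alpha 0.05; true difference 0.5 SD; Veterans independent unless stated.

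**Variance of the between-arm difference.**
- Post score: 2/n
- Change score or group-by-time term: 2(1−ρ) × 2/n
- ANCOVA: (1−ρ²) × (2/n) × (1 + 1/(2n−4)); the last factor is the small-sample cost of estimating the slope

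Example at n = 20, ρ = 0.5: post 0.100; change 2 × 0.5 × 0.1 = 0.100; ANCOVA 0.75 × 0.1 × (1 + 1/36) = 0.0771. The ratio is 0.77 to either.

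Results at 20 per arm (half-widths from t with 2n−2 df, or 2n−3 for ANCOVA; power from the noncentral t):

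| | ρ = 0.3 | ρ = 0.5 | ρ = 0.7 |
|---|---|---|---|
| ANCOVA/post variance | 0.94 | 0.77 | 0.52 |
| ANCOVA/change variance | 0.67 | 0.77 | 0.87 |
| 95% CI half-width, post (SD) | 0.64 | 0.64 | 0.64 |
| 95% CI half-width, change | 0.76 | 0.64 | 0.50 |
| 95% CI half-width, ANCOVA | 0.62 | 0.56 | 0.46 |
| Power, post | 34% | 34% | 34% |
| Power, change | 26% | 34% | 51% |
| Power, ANCOVA | 36% | 42% | 57% |

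At 16 per arm (also 20 per arm with an assumed 80% survey return) and ρ = 0.5, the half-width falls from 0.72 to 0.64 SD and power rises from 28% to 34%.

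**Simulation check.** In 40,000 simulated trials at n = 20, ρ = 0.5, the standard errors were 0.318 (post), 0.315 (change) and 0.277 (ANCOVA), against 0.316, 0.316 and 0.278 from the formulas.

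**Break-even.** ANCOVA loses to a post-score test only if ρ < √(1 − 1/(1 + 1/(2n−4))), which is 0.16 at n = 20 and 0.19 at n = 16. It loses to a change score only if ρ > 2/(1 + 1/(2n−4)) − 1, which is 0.95 and 0.93. At ρ = 0 the cost against a post-score test is 1/36 = 2.8% or 1/28 = 3.6% of variance.

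**Correlation within classes.** A class effect arising after baseline adds (m−1) × ICC × 2/n to every variance. With m = 10, an assumed ICC of 0.05 and n = 20, that is 9 × 0.05 × 0.1 = 0.045. At ρ = 0.5: post and change 0.145, ANCOVA 0.1221, ratio 0.84. Twenty per arm is then worth 20 × 0.145/0.1221 ≈ 24 per arm, rather than 0.100/0.0771 × 20 ≈ 26. In simulation of this setting, the ordinary 95% interval covered about 88% of the time for ANCOVA and about 90% for the post-score t-test.

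**Effect-size scale.** Relative to the unadjusted SD, the change-score SD multiplies the effect by 1/√(2(1−ρ)) = 0.85/1.00/1.29, and the residual SD by 1/√(1−ρ²) = 1.05/1.15/1.40, at ρ = 0.3/0.5/0.7. A difference of 0.5 raw SD therefore appears as 0.42 or 0.65 on the change-score scale at ρ = 0.3 or 0.7. In a standard two-sample formula (80% power, n = 2(1.96 + 0.84)²/d²) these give about 88 or 38 per arm, against 63 on the raw scale.

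**The case against.** The strongest case against is materiality. The plan's primary focus is reach and sustained engagement (Program Initiation and Participation), and Hypothesis 1 concerns initiation and participation. The survey scores are secondary, the sample is a pilot's, and an effect size with a half-width of 0.56 SD is little better for powering a trial than one with 0.64. The 0.5 SD difference is also generous between two programs that share most of their poses; at an assumed 0.2 SD (20 per arm, ρ = 0.5), power moves only from 9.5% to 10.8%. All of this stands. It limits the size of the point but does not remove it, because the change costs almost nothing and the plan itself commits to using these effect sizes.

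A reader might infer that the plan ignores baseline. The text does not support that: the form is unstated, and a change-score or repeated-measures reading, which does use baseline, is open. On that reading the saving at ρ = 0.7 is only about 13% of variance.

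A reader might also infer that the planned comparison is biased. Under randomization it is not; the loss is one of precision. Any new bias risk lies with the adjusted analysis. A baseline completed at the first class comes after the Veteran has turned up for a particular program. If knowing the assignment shifts self-reported scores, adjusting for them can bias the contrast, whereas an unadjusted post-score comparison avoids this. Dropping such Veterans is no remedy, because only first-class attendees can complete a survey there, so the exclusion would depend on behavior after randomization. This objection stands and shapes the fix.

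The mismatch between pain interference and pain behavior is a separate drafting matter. It adds no weight to the case for ANCOVA.

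**Conclusion.** The point holds as a modest precision gain on secondary outcomes, together with an undefined effect-size scale. Whichever form the team intends, ANCOVA is more precise for ρ between 0.3 and 0.7, with variance 0.52 to 0.94 of a post-score test and 0.67 to 0.87 of a change score at 20 per arm. The gain over post scores is small at ρ = 0.3, and class correlation shrinks it further. These figures rest on assumed ρ, equal SDs and full survey return; the documents give none of these.

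Two stronger conclusions are not supported. Initiation and attendance are unaffected. Nor does ANCOVA make the pilot's effect sizes a firm basis for power: the interval is still ±0.56 to 0.64 SD at ρ = 0.5, and wider if classes are correlated. It is worth fixing because the data are already planned and the effect-size scale has to be settled whichever test is used.

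**What to change.** In Quantitative Analysis of Surveys:

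- Make the between-arm analysis of each continuous score an ANCOVA of post score on randomized arm and baseline score, with Veterans in their assigned arm. Medication and other-program use need a different model.
- Report the adjusted difference with 95% CI, the effect size standardized by the unadjusted (pooled baseline) SD, and the observed baseline-to-post correlation.
- State that the interval assumes independent Veterans and is too narrow if classes are correlated.
- Record whether each baseline survey preceded disclosure of assignment, whatever the route of completion. As sensitivity analyses, report the unadjusted post-score difference, and an ANCOVA that keeps every Veteran but treats post-disclosure baselines as missing, filled with the mean of both arms combined.
- Add pain interference to the list of compared outcomes, and reconcile it with pain behavior there, in the survey list and in Table 1.

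The cost is SAP wording, one regression per continuous score and one recorded date per Veteran; no new questionnaire is needed. The statistical downsides are one degree of freedom (about 3-4% of variance if ρ is near 0) and possible bias if post-disclosure baselines are shifted by knowledge of the assignment, which the two sensitivity analyses check.

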During the beginning months of the study we will hold a series of meetings with our yoga teachers, research team and advisory panel members, to finalize the curriculum, music play-lists and scheduling (day of the week and time of the day) of the classes; however, yoga poses that are known to benefit individuals who experience chronic low back pain will comprise the poses used in each program. These poses already comprise much of Hatha yoga classes, and we do not anticipate that finalizing the curriculum for either program will be significantly time-intensive.

Participating in the Rage Against the Pain and treatment as usual (Hatha yoga) interventions will entail following along with the yoga poses and corresponding breath work (e.g., suggestions for when to inhale and exhale commensurate with the movement) being cued by the instructor. Veterans will be clearly cued about options for modification for every pose, including options to modify poses using a chair or the wall; Veterans who are unable to engage in a modified version of any pose will be instructed to take child's pose or rest in a chair, against the wall or on the floor during that pose. When the set of movements for each class has been run through, the class will engage in a culminating activity (meditation referred to savasana or

or cool down, see below) wherein Veterans will be instructed to sit in chairs or lay on the floor with their eyes closed to relax. Veterans will be asked to complete practice logs in class.

We will also share a training manual with our Veteran participants (along with a yoga mat, strap and set of blocks) and encourage them to engage in home practice (ideally, about half an hour three times per week in addition to the weekly group classes).²

Treatment as Usual. The 'treatment as usual' class will be conducted in the style of the yoga classes currently being offered to Veterans at the Hines VA Hospital, which is a program akin to Hatha yoga with chair modifications available to all Veterans who choose/need to use them (described above).

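### The larger trial's power is to be based on effect sizes observed in 16-20 Veterans per arm, too imprecise for that use, and the plan does not say which comparison's effect size is meant

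*Combined protocol and SAP*

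**What the plan says.** Under Data Analyses (Quantitative Analysis of Surveys), the team "will base power calculations off of the effect sizes on key outcomes (e.g., pain intensity, interference, back-pain related function) observed in this pilot". This is the only sentence that says how the pilot feeds the next power calculation. The same section, and Enrollment and Sample Size, give the goal for aims 2 and 3 in softer terms: "estimates of effect sizes to inform power considerations for the next step, the larger trial".

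The target is "16-20 Veterans in RAP and another 16-20 Veterans in the Hatha yoga program".

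On the comparisons, the section says "We will use bivariate analyses (t-tests) and ANOVA to compare outcomes" and lists two kinds: "1) for each Veteran before and after program participation, and (2) between Veterans in the RAP vs. traditional yoga programs". It adds a comparison of all outcomes by gender, and then says "We will calculate effect sizes for all bivariate comparisons". None of these is singled out for the power calculation.

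Other inputs for the larger trial are already planned: "We will use our adoption and participation rates to base recruitment and enrollment targets for that trial".

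On content, Intervention Details says "yoga poses that are known to benefit individuals who experience chronic low back pain will comprise the poses used in each program", and the Rage Against the Pain paragraph says that its curriculum follows that of the Hatha classes.

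**The concern.** There are two problems.

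- **Precision.** The required sample size varies with 1/d². A pilot estimate that is high by chance gives a next trial that is too small. An estimate of zero gives no sample size at all, and a negative one sizes a trial for the opposite direction. The plan names no confidence limit, sensitivity range or target difference for this calculation. The 30% reduction on the Roland-Morris questionnaire, in the survey section, is a within-person criterion and is not tied to power. The Limitations do not mention imprecision.
- **Ambiguity.** Two programs built on the same poses could both improve from before to after with little or no difference between them. A pre-post effect size then says nothing about how many Veterans a between-program comparison needs.

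What is at stake is the size of the next trial, which the plan makes a goal of aims 2 and 3.

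**Working it through.** **The plan's own figure.** Class Size gives two sessions of each program with 8-10 Veterans in each: 2 × 8 = 16 to 2 × 10 = 20 per program, and 32-40 over both. This matches Enrollment and Sample Size. The documents give no power, alpha, SD, effect size or attrition rate, so there is no power calculation to reproduce.

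**Precision of the between-arm d.** Near d = 0, SE = √(2/n) and the 95% half-width is 1.96 × SE.

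| n per arm | SE | half-width |
|---|---|---|
| 20 | 0.316 | 0.62 |
| 16 | 0.354 | 0.69 |
| 13 (16 less an assumed 20%) | 0.392 | 0.77 |

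These figures assume independent outcomes. Any correlation within classes of 8-10 would widen them. Baseline adjustment, which the section does not name, would narrow them by √(1 − r²). With an assumed pre-post correlation r of 0.5 to 0.7, the half-width runs from 0.620 × √(1 − 0.49) = 0.44 (20 per arm, r = 0.7) to 0.693 × √(1 − 0.25) = 0.60 (16 per arm, r = 0.5), in raw SD units.

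**What this does to the sample size.** Assume two-sided alpha 0.05, 80% power and 1:1 allocation, so that n per arm = 2 × (1.96 + 0.84)² / d² ≈ 15.7 / d². Suppose the pilot shows d = 0.3. The exact 95% interval is −0.40 to 0.99 with 16 per arm and −0.33 to 0.92 with 20.

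- At the point estimate: 15.7 / 0.09, or 175 per arm.
- At the upper limit: 16 per arm (16-per-arm pilot) or 19 per arm (20-per-arm pilot).
- At the lower limit: no sample size, because the sign has reversed.

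**Chance of a zero or wrong-direction estimate.** This is Φ(−d√(n/2)). For an assumed true d of 0.3:

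- n = 20: Φ(−0.3 × √10) = Φ(−0.949) = 0.171
- n = 16: Φ(−0.3 × √8) = Φ(−0.849) = 0.198

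For other assumed true values (20 to 16 per arm) it is 26-29% at d = 0.2, 6-8% at 0.5 and about 1% at 0.8.

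**Which effect size.** As an illustration, sizing on a pre-post d of 0.5 gives 15.7 / 0.25, or 63 per arm. For a true between-arm d of 0.3, the power of that trial is Φ(0.3 × √31.5 − 1.96) = Φ(−0.28) = 39%, where 175 per arm are needed. For a true between-arm d of 0.2 it is Φ(0.2 × √31.5 − 1.96) = Φ(−0.84) = 20%, where 393 per arm are needed.

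**Illustration of under-sizing.** Suppose one unadjusted point estimate were entered directly into a formula for an individually randomized two-arm superiority trial. True power falls below 50% when the pilot estimate exceeds about 1.43 times the true d (2.80 / 1.96), which is 0.43 for a true d of 0.3. From the noncentral t distribution the chance is 35% (20 per arm) to 36% (16 per arm). It is 40-41% at a true d of 0.2, 25-28% at 0.5 and 16-19% at 0.8.

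**The case against.** Four objections have force.

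- **It concerns another trial.** The primary focus here is reach and sustained engagement, and the larger trial will need its own sample-size justification. This is true and limits the weight of the point. Still, the plan commits to the method now, and a target difference chosen before the pilot outcomes are seen is more credible than one chosen after.
- **The plan does not say that one raw point estimate goes into a formula.** It speaks of effect sizes in the plural, and elsewhere only of informing power. A reader might infer that the plan rules out confidence limits or conservative values. It does not; it is silent on them. But the one operative sentence makes the observed effect the basis, and nothing elsewhere qualifies it.
- **The under-sizing percentages depend on assumptions and do not measure the benefit of the fix.** This stands. If the pre-specified important difference were d = 0.5, the same formula gives 63 per arm and only 39% power at a true d of 0.3. The case for a pre-specified difference is that smaller effects need not be detected, not that true power is always higher.
- **Between-arm is the natural reading.** The pilot randomizes RAP against Hatha, and Hypothesis 1 compares the two programs. A reader might infer that the team intends to size the larger trial on pre-post change. The documents do not say so, and they do not state that trial's design. What remains is an ambiguity that a short clarification removes.

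**Conclusion.** The point holds in a limited form: a cheap improvement that should be made, not an error that affects the pilot. An unadjusted between-arm effect size from 16-20 per arm carries a 95% half-width of about 0.62-0.69, assuming full follow-up and independent outcomes. That is wide enough for the estimate to be zero or in the wrong direction in 17-20% of pilots if the true d were 0.3. It should not be the basis for sizing the next trial, and the plan should say which comparison is meant.

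A reader might take the 35-36% chance of a next trial with under 50% power as a forecast. The documents do not support that. It needs an assumed true effect, design, alpha and planned power, and direct use of a single unadjusted estimate, none of which the plan states. Nor does the small pilot count as a fault in itself: estimating effect sizes is a declared goal, and the weakness lies only in what they are then used for.

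**What to change.** Replace the sizing clause in Quantitative Analysis of Surveys with:

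> Power for the larger trial will be based on a between-program difference judged important and specified in advance for its primary outcome, not on the pilot point estimate. The pilot will supply the SD (with its uncertainty shown in a sensitivity range), the pre-post correlation and attrition, in addition to adoption and participation rates. Between-arm effect sizes will be reported with 95% confidence intervals, and within-arm pre-post effect sizes will not be used to size a between-program comparison.

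The goal wording for aims 2 and 3, here and in Enrollment and Sample Size, can stay if *with 95% confidence intervals* is added after the mention of effect sizes.

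**Cost.** No new data are needed and no pilot analysis is lost. The team must justify a target difference from sources outside this document, and the next trial may be larger. As one example of a sensitivity range, the one-sided 80% upper limit for the SD is √(df / χ²₀.₂₀) times the observed SD: 1.116 with 20 per arm (df 38) and 1.133 with 16 per arm (df 30). Squared, these raise the sample size by 24% and 28%. The choice of limit is for the team.
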